11.8 Anticipated or Unanticipated

If an AE is determined to be related to the study device the sponsor will then assess the event to determine if it is anticipated or unanticipated.

- **Anticipated:** the event is identified in the CIP; labeling; report of priors/ IB or user guide.
- **Unanticipated:** the event has not been previously identified in the CIP; labeling; report of priors/ IB or user guide.

12. Data Review Committees

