 Risks with hypoglycemia may include: Seizure Coma Altered mental status Loss of consciousness Cardiovascular event Death Risk of rebound hyperglycemia with ketosis 	 Prevention and mitigation include: Follow the provided user guides for insulin pump management. Parent(s)/guardian(s)/companion(s) should be present at night with subjects. Parent(s)/guardian(s) will be trained on study device and diabetes management principles and instructed to call investigator with problems. Companions will be trained on diabetes management principles and emergency response training. Parent/caregivers and companions should also be present during meal and exercise challenges. Train prior to study device use on appropriate device use and diabetes management principles and instruct to call investigator with problems. Instruct to check their meter glucose if their low symptoms do not match their sensor alerts or SG readings in order to make diabetes treatment decisions. Instruct to check their meter glucose if there are any concerns that the SG value is not accurate). Instruct to have glucose and glucagon on hand for hypoglycemia.
Risk with Sensors	Prevention and Mitigation
 Risks with sensors may include: Skin irritation or reaction to adhesives Bruising Discomfort Redness Bleeding Pain Rash Infection Irritation from tapes used with glucose-sensing products Raised bump Appearance of a small "freckle-like" dot where needle was inserted Allergic reaction Syncopal episode secondary to needle insertion Soreness or tenderness Swelling at insertion site Sensor fracture, breakage or damage Minimal blood splatter associated with sensor needle removal 	 Prevention and mitigation include: Follow the provided user guides for insertions and care of sensors. If a sensor site becomes infected or inflamed, the sensor will be removed and another placed in a new location. Instruct to check their meter glucose if their high or low symptoms do not match their sensor alerts or SG readings in order to make diabetes treatment decisions. Instruct to check their meter glucose if there are any concerns that the SG value is not accurate. Instruct if there are no sensor values, no treatment decisions will be made until a BG is confirmed.

CIP336 Clinical Investigatio	n Plan
D00459338 Version	n E Page 98 of 159 Medtronic

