Any serious adverse effect on health or safety or any life-threatening problem or death caused by, or associated with, a device, if that effect, problem, or death was not previously identified in nature, severity, or degree of incidence in the investigational plan or application (including a supplementary plan or application), or any other unanticipated serious problem associated with a device that relates to the rights, safety, or welfare of subjects.

Unanticipated Serious Adverse Device Effect (USADE) (ISO 14155:2020)

Serious adverse device effect which by its nature, incidence, severity or outcome has not been identified in the current risk assessment.

Note 1 to entry: Anticipated serious adverse device effect (ASADE) is an effect which by its nature, incidence, severity or outcome has been identified in the risk assessment.

Serious Health Threat (ISO 14155:2020)

Signal from any adverse event or device deficiency that indicates an imminent risk of death or a serious deterioration in the health in subjects, users or other persons, and that requires prompt remedial action for other subjects, users or other persons

Note 1 to entry: This would include events that are of significant and unexpected nature such that they become alarming as a potential serious health hazard or possibility of multiple deaths occurring at short intervals.

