12.2 Data Monitoring Committee

A data monitoring committee (DMC) consisting of external physicians with an expertise in Endocrinology and the management of insulin-requiring diabetes including CGM, along with an external statistician will be convened to review study progress and safety. The Board will convene approximately every 90 days. The Board will also meet when ad hoc review is required.

The DMC will perform 4 main functions:

First: DMC will track and trend the overall safety of the study. Event rate, defined as number of events per 100 patient years will be reviewed by the DMC with respect to the following:

- Event rate of all SAEs
- Event rate of severe hypoglycemia
- Event rate of severe hyperglycemia
- Event rate of DKA
- Event rate of device related AEs

CIP336 Clinical Investigation Plan Medtronic D00459338 Version E Page 114 of 159

Second: Based on their meetings, DMC will recommend a decision to the sponsor regarding the following:

- Whether or not enrollment should be halted.
- Whether or not the entire study will need to be stopped including for those subjects who have received study devices already.

Note: If it is decided to withdraw subjects from participation in the study or if the study is stopped, subjects will be followed-up in accordance with standard practice by their own providers.

Third:

During the study, the following steps will be taken for:

- Unanticipated adverse device effects (UADE)
- Unanticipated Serious Adverse Device Effects (USADE)
- Device related DKA
- Device related severe hypoglycemia

DMC is to meet within 10 days from the time that the CEC adjudicates an event as one of the above. If possible, the investigator should be available to answer questions by DMC.

Based on their meeting, DMC will recommend a decision to the sponsor regarding the following:

- Whether or not enrollment should be halted.
- Whether or not the entire study will need to be stopped including for those subjects who have received study devices already.

Note: If it is decided to withdraw subjects from participation in the study or if the study is stopped, subjects will be followed-up in accordance with standard practice by their own providers.

Fourth: The DMC will review Safety data and provide a recommendation to the sponsor regarding staged enrollment of pediatric subjects:

The DMC will provide a recommendation to proceed with the following staged enrollment:

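### Section 11.8 treats a device-related event as anticipated once it is named, without the severity, incidence and outcome criteria of Section 11.2, so some serious device effects could stay off the expedited pathway

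*Protocol*

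**What the plan says.** Section 11.8 applies once an adverse event has been judged device-related: "the sponsor will then assess the event to determine if it is anticipated or unanticipated". The event is anticipated when "the event is identified in the CIP; labeling; report of priors/ IB or user guide" and unanticipated when "the event has not been previously identified in the CIP; labeling; report of priors/ IB or user guide". Neither bullet refers to severity, frequency or outcome.

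Section 11.2 gives the definitions:

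- **UADE** (from 21 CFR 812): a serious effect that "was not previously identified in nature, severity, or degree of incidence in the investigational plan or application".
- **USADE** (from ISO 14155): "Serious adverse device effect which by its nature, incidence, severity or outcome has not been identified in the current risk assessment".
- **ASADE**, its anticipated counterpart: one that "is an effect which by its nature, incidence, severity or outcome has been identified in the risk assessment".

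Table 7 in Section 11.6 makes the sponsor responsible for assigning UADE or USADE status. Sections 12.1 and 12.2 then attach short timelines to four kinds of event: UADE, USADE, device-related DKA and device-related severe hypoglycemia.

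**The concern.** The protocol contains two tests for the same question, and they can give different answers. Section 11.8 is the only place that describes the decision as a step the sponsor carries out, and it is the looser of the two. Table 6 names a long list of serious outcomes, so a test that stops at whether an event is named will often return anticipated.

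What is at stake is speed and visibility. A listed serious device effect that turns out worse, or more common, than identified is the kind of signal that the incidence and severity criteria in 11.2 are there to catch. If 11.8 settles its status, the accelerated steps need not start and the event does not appear in the UADE or USADE lines of the safety summary (Protocol 14.5.4; SAP 7.9.7 and 7.10).

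**Working it through.** No arithmetic applies beyond a count of triggers. The check compares the tests and then traces what depends on the result.

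**Step 1: the tests side by side**

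| | Criteria | Reference documents |
|---|---|---|
| 11.8 | Event named or not | Protocol, labeling, prior-investigation report or brochure, user guide |
| 11.2 UADE | Nature, severity, degree of incidence | Investigational plan or application |
| 11.2 USADE and ASADE | Nature, incidence, severity, outcome | Risk assessment |

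Section 11.8 keeps, at most, the nature criterion. It also looks in a different set of documents from either definition in 11.2.

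**Step 2: where the answers diverge**

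- *Serious device-related hyperglycemia short of DKA.* Table 6 names hyperglycemia from occlusion, site failure and under-delivery, so under 11.8 it is anticipated however often it occurs. Under 11.2, a frequency above what was identified can make the serious cases unanticipated.
- *A site infection worse than described.* Table 6 lists localized infection for infusion sets and infection for sensors. Under 11.8 the name is enough. Under 11.2 the severity must also have been identified.

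**Step 3: what depends on the call**

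| Step | Section | Depends on anticipated status? |
|---|---|---|
| FDA notice, about 72 hours (US) | 12.1 | Yes for UADE and USADE; no for device-related DKA and severe hypoglycemia |
| CEC adjudication, 10 days | 12.1 | Same |
| DMC meeting: "DMC is to meet within 10 days from the time that the CEC adjudicates an event as one of the above" | 12.2 | Same |
| UADE report to sponsor and IRB, 10 working days (US) | 11.5 | Yes |
| UADE and USADE summary lines | 14.5.4; SAP 7.9.7, 7.10 | Yes |

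Two of the four expedited triggers depend on the call and two do not. Any serious device effect other than DKA or severe hypoglycemia can reach the expedited steps only through UADE or USADE status.

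**Step 4: what such an event would still receive**

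Sites report every SAE and SADE to the sponsor, ideally within 24 hours (11.4). The CEC reviews SAEs, SADEs and severe hyperglycemia (12.1), but no deadline is stated for that wider list. The DMC reviews rates of SAEs, severe hyperglycemia and device-related events about every 90 days and can meet ad hoc (12.2).

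**Step 5: whether a later review would repair a wrong call**

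Only in part. The CEC's stated task is to agree or disagree with the investigator's classification, whereas Table 7 gives UADE and USADE status to the sponsor. Whether an event was unanticipated is something the CEC may look at, not something it must. The FDA clock runs about 72 hours from knowledge of the event, while the CEC has 10 days even on its accelerated path, so a CEC correction could come after the notice was due.

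**The case against.** The strongest reply is that 11.2 remains in force. It says the sponsor uses the ISO 14155 and 21 CFR 812 definitions, Table 7 has the sponsor classify UADE and USADE in those terms, and 11.8 mentions neither and does not claim to replace them. This stands in part: misclassification follows only if 11.8 is applied alone. It does not remove the conflict, because 11.8 uses the same pair of words with a different test and no cross-reference.

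A second reply is that for many named outcomes the two tests agree. This also stands. Table 6 lists "Loss of consciousness Cardiovascular event Death" among the risks of hypoglycemia, so that outcome is already identified. A device-related death from hypoglycemia would ordinarily also be a device-related severe hypoglycemia, with its own trigger. Section 11.3 gives hospitalised insertion-site cellulitis as an example of a SADE, so an infection of that severity is identified too. The divergence concerns events beyond what is described, in degree or in frequency.

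A third reply points to the backstops in 11.4, 12.1 and 12.2. Table 10 adds a 72-hour incident report for Canadian investigators that is not conditioned on UADE status. These limit the harm, but they do not supply the US notice or the CEC and DMC deadlines.

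Three stronger readings are tempting and are not supported:

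- A reader might infer that all worse-than-expected serious device harm escapes expedited review. Two of the four triggers rule that out.
- A reader might infer that the UADE and USADE lines would be nearly empty. Since 11.2 still applies and both tests agree on many outcomes, the documents do not show this.
- A reader might try to size the problem from the severe hyperglycemia rate in Table 8. That rate is for ages under 15, whereas the cohort is 7-17, and the protocol's definition of severe hyperglycemia requires neither seriousness nor device causation. It is no benchmark for serious device-related events.

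**Conclusion.** The point holds in a limited form. Sections 11.8 and 11.2 state conflicting criteria and name different reference documents. Read literally, 11.8 could keep a listed serious device effect, other than DKA or severe hypoglycemia, off the expedited pathway when it is more severe or more frequent than identified. The reach is two of four expedited triggers, the US UADE report and the UADE and USADE summary lines. It does not affect the HbA1c or glucose endpoints, their hypotheses or the sample size.

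The conclusion assumes that staff follow 11.8 as worded, without going back to 11.2. The documents make that possible but not certain. How many events would be affected cannot be estimated, because no expected rate of serious device-related events by type is given, and the risk assessment, labeling and brochure are not part of these documents.

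**What to change.** Amend Section 11.8 to say that:

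- for serious device effects, anticipated or unanticipated status is decided by the UADE and USADE/ASADE definitions in 11.2, covering nature, severity, incidence and outcome as each definition requires, against the reference documents named there;
- being named in the protocol or labeling is not sufficient;
- the listing test continues to apply to non-serious device-related events.

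In Section 12.1, state that the CEC uses the same test when it considers whether an event was unanticipated.

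The restriction to serious effects is deliberate. Table 6 gives no incidences, so requiring an identified incidence for every device-related event could turn many non-serious events into unanticipated ones. The sponsor should also confirm that the risk assessment and application give severities and incidences specific enough to apply 11.2.

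The cost is a few lines in a protocol amendment, with no change to visits, data collection or analysis. The downside is small: a few more serious events may need expedited handling.

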12.1 Clinical Events Committee

A clinical events committee (CEC) consisting of external physicians with an expertise in endocrinology and the management of diabetes including insulin pumps and CGM will be convened. The CEC will review AEs as required per protocol, which include reports of:

- Serious adverse event
- Serious adverse device effect
- Unanticipated adverse device effect
- Unanticipated serious adverse device effect
- Severe hypoglycemia
- Diabetic ketoacidosis
- Severe hyperglycemia

During the study, the following steps will be taken for:

• Unanticipated adverse device effects (UADE)

- Unanticipated Serious Adverse Device Effects (USADE)
- Device related DKA
- Device related severe hypoglycemia

US Only: Sponsor will notify Food and Drug Administration (FDA) within approximately 72 hours of knowledge of the event and provide updates to those regulatory authorities as information becomes available.

Canada only: Sponsor will notify local regulatory authorities as information becomes available per local requirements.

CEC is to review and adjudicate the event within 10 days from the time that the sponsor is notified.

The CEC will assess events to determine agreement or disagreement with the investigator classification of an event.

If the CEC disagrees with the investigator's classification of the event, the rationale will be provided to the investigator. If the investigator agrees with the CEC's adjudication, the CRF documenting the AE will be updated accordingly.

If the investigator does not agree with the CEC's adjudication classification, both determinations will be provided within the final report; however, the CEC's adjudication will be used for data analysis. The disagreement will also be included in reporting to IRBs/ ECs and regulatory authorities, if required.

The CEC may review applicable information for device related AEs which may include:

- Whether or not the event was unanticipated
- Review of sensor data from CareLink Personal/CareLink system software report (when applicable)
- Review of pump data from CareLink Personal/CareLink system software report (when applicable)
- Misuse of the device by the user

Review of events may require the following information. Final disposition may be delayed based on obtaining this information:

- Monitoring by sponsor at investigational center
- Device return and failure analysis
- CareLink Personal/CareLink system software upload and review of software reports
- Subject clarification to investigational center regarding details about the event

• Source documents that support event: Paramedic records; ER records; Lab records; Hospital admission and discharge summary

The following factors should be carefully considered in the CEC's recommendation to sponsor:

CIP336 Clinical Investigation Plan			
D00459338	Version E	Page 113 of 159	Medtronic

- 1. Was the severe hypoglycemia or DKA related to the AHCL algorithm, or was it related to a known insulin pump risk? For example, a question that may be considered in DKA would be whether the event was related to an infusion set issue or caused by the AHCL algorithm.
- Another important consideration would be if the severe hypoglycemia, severe hyperglycemia or DKA event was related to a device malfunction versus patient non-compliance. For example, if a software anomaly leading to an under-delivery of insulin is discovered versus the subject repeatedly ignoring alarms prompting the subject to take action.
- 3. Severe hypoglycemia, severe hyperglycemia or DKA caused directly by an infusion set issue when the study pump is functioning as intended would likely result in acceptance to proceed with the study versus severe hypoglycemia or DKA that are directly caused by the AHCL algorithm or a device malfunction might stop study enrollment or entire study altogether.
- 4. It should be noted that the final determination of causality related to 780G system that is made by the CEC may include additional factors which the members consider to be clinically relevant and important.

12.2 Data Monitoring Committee

A data monitoring committee (DMC) consisting of external physicians with an expertise in Endocrinology and the management of insulin-requiring diabetes including CGM, along with an external statistician will be convened to review study progress and safety. The Board will convene approximately every 90 days. The Board will also meet when ad hoc review is required.

The DMC will perform 4 main functions:

First: DMC will track and trend the overall safety of the study. Event rate, defined as number of events per 100 patient years will be reviewed by the DMC with respect to the following:

- Event rate of all SAEs
- Event rate of severe hypoglycemia
- Event rate of severe hyperglycemia
- Event rate of DKA
- Event rate of device related AEs

CIP336 Clinical Investigation Plan Medtronic D00459338 Version E Page 114 of 159

Second: Based on their meetings, DMC will recommend a decision to the sponsor regarding the following:

- Whether or not enrollment should be halted.
- Whether or not the entire study will need to be stopped including for those subjects who have received study devices already.

Note: If it is decided to withdraw subjects from participation in the study or if the study is stopped, subjects will be followed-up in accordance with standard practice by their own providers.

Third:

During the study, the following steps will be taken for:

- Unanticipated adverse device effects (UADE)
- Unanticipated Serious Adverse Device Effects (USADE)
- Device related DKA
- Device related severe hypoglycemia

DMC is to meet within 10 days from the time that the CEC adjudicates an event as one of the above. If possible, the investigator should be available to answer questions by DMC.

Based on their meeting, DMC will recommend a decision to the sponsor regarding the following:

- Whether or not enrollment should be halted.
- Whether or not the entire study will need to be stopped including for those subjects who have received study devices already.

Note: If it is decided to withdraw subjects from participation in the study or if the study is stopped, subjects will be followed-up in accordance with standard practice by their own providers.

Fourth: The DMC will review Safety data and provide a recommendation to the sponsor regarding staged enrollment of pediatric subjects:

The DMC will provide a recommendation to proceed with the following staged enrollment:

The enrollment of subjects 7-17 years of age will not move forward until 10 subjects 18 years or older have completed 30 days of the study period and the Data Monitoring Committee (DMC) has determined that it is safe for 7-17 year olds to be enrolled into the study.

General guidance for DMC's recommendations to sponsor should be based on the following:

In general, a DMC recommendation regarding study stoppage or resumption of enrollment should be made to the sponsor within 1 week of the DMC meeting where the determination is made. However, if more data is needed, the DMC may meet again to re-assess their decision within 2 weeks or when required data becomes available.

D00459338 Version E Page 115 of 159 Medtronic

In their recommendation to the sponsor, the DMC may take into account the thresholds listed below for the number of subjects experiencing hypoglycemia requiring assistance from another person or DKA to identify when the number of subjects experiencing these events exceeds the number that would be anticipated for the study population over the duration of this study. These thresholds should be interpreted with caution due to potential differences in study populations and study design.

- a. Rates taken from type 1 exchange (Cengiz et. Al, and Weinstock et. Al), are higher than the clinical studies STAR 3, 530G adult in-home study (CEP266) and 530G Pediatric inhome study (CEP287).
- b. Reasons for lower rates of severe hypoglycemia and DKA in the clinical studies mentioned could be related to several factors including but not limited to the exclusion of those with DKA or severe hypoglycemia, additional attention secondary to mandatory study visits, selection bias of motivated patients willing to perform study procedures and access to free study devices during the course of the study.
- c. The DMC should consider stopping study if rates of severe hypoglycemia and DKA are significantly worse (e.g., higher) in AHCL than rates provided by clinical trials mentioned in **Table 8**.
- d. Age consideration may also be factored in by the DMC. For example, severe hypoglycemia rates in those >25 years may be higher than those 25 years and below.
- e. Should DKA and/or severe hypoglycemia occur early in the study, the DMC should consider that the higher event rate may not necessarily represent a significant safety concern.

D00459338

Table 8. Hypoglycemia/ Hyperglycemia/ DKA Threshold

Adverse Event	Reference	Reference Rate > 25 years old	Reference Rate 15-25 years old	Reference Rate <15 years old
Severe Hyperglycemia events per 100 patient years	CER 302	NA	NA	71.64
	STAR 3 Bergenstal et. al	SAP arm: 0.68 Control arm: 0	SAP arm: 2.7 Control arm: 3.6	SAP arm: 2.2 Control arm: 0
DKA events per	530G Adult in-home study CEP 266 (MDT on file)	1.27	3.4	N/A
100 patient years	Pediatric in-home study CEP 287 (MDT on file)	N/A	N/A	0
	Type 1 exchange Weinstock et. al	4.8	N/A	N/A
	Type 1 exchange Cengiz et. al	N/A	9.9	9.9
	_			
	STAR 3 Bergenstal et. al	SAP arm: 16.5 Control arm: 20.9	SAP arm: 5.4 Control arm: 3.9	SAP arm: 10.2 Control arm: 3.6
Severe hypoglycemia	530G Adult in-home study CEP 266 (MDT on file)	0.85	0	N/A
per 100 patient years	530G Pediatric in-home study CEP 287 (MDT on file)	N/A	N/A	1.42
	Type 1 exchange Weinstock et. al	11.8	N/A	N/A
	Type 1 exchange Cengiz et. al	N/A	6.2	6.2

Severe hypoglycemia and DKA event rates were taken from the following:

- 1. Richard Bergenstal et.al: Effectiveness of Sensor-Augmented Insulin-Pump Therapy in Type 1 Diabetes. New England Journal of Medicine, 2010; 363:311-20
- 2. Weinstock et. al: Severe hypoglycemia and diabetic ketoacidosis in adults with type 1 diabetes: results from the T1D Exchange clinic registry. J Clin Endocrinol Metab. 2013 Aug;98(8):3411-9.
- 3. Cengiz et. al: Severe hypoglycemia and diabetic ketoacidosis among youth with type 1 diabetes in the T1D Exchange clinic registry. Pediatr Diabetes. 2013 Sep;14(6):447-54.
- 4. MDT on file: Statistical Analysis Plan (SAP) for CEP304, 056-F286

13. Device Deficiencies and Troubleshooting

The subjects will be instructed to contact the investigational center staff for questions or concerns regarding study devices.

All DDs reported directly to the investigational center staff by a subject and those experienced by the investigational center staff will be reported on the appropriate eCRF in a timely manner. In addition, an eCRF should also be completed by the investigational center staff for each reported DD that did not lead to an Adverse Event. A DD that results in an AE should be captured on an AE CRF only.

Subjects participating in the study are expected to have mild irritation from device wear at times. Only discomfort occurring at a threshold resulting in early removal of the device should be reported as a DD or adverse event.

Device Deficiency (ISO 14155:2020)

A device deficiency is any inadequacy of a medical device with respect to its identity, quality, durability, reliability, usability, safety, or performance.

Note 1 to entry: Device deficiencies include malfunctions, use errors, and inadequacy in the information supplied by the manufacturer including labeling.

Note 2 to entry: This definition includes device deficiencies related to the investigational medical device or the comparator.

Each DD will be assessed for SADE potential defined as:

- A DD that did not lead to an Adverse Event, but could have led to a SADE:
 - a) if either suitable action had not been taken,
 - b) if intervention had not been made, or
 - c) if circumstances had been less fortunate

CIP336 Clinical Investigation Plan			
D00459338	Version E	Page 118 of 159	Medtronic

To return a study device as part of a DD, the subject is to contact the investigational center staff, and the investigational center staff should then follow the study procedures for returning products with DDs. For a list of study devices that needs to be return to the sponsor, please consult your study materials.

It is the responsibility of the investigator to follow their EC/IRB reporting requirements.

14. Statistical Design and Methods

